Appendix 2 also provides a summary of these pre-treatment evaluations

9.0 TREATMENT/INTERVENTION PLAN

Patients will receive 2 phases of therapy, as described below.

9.1.0 FIRST PHASE: RADIATION THERAPY & CETUXIMAB

Cetuximab will be given at 250 mg/m2/weekly for 6 doses. On days when both the radiation therapy and cetuximab are administered, there is no mandated order of administration or timing between the 2 treatments. Regardless of the order of administration, it is important to note that the patient should be carefully monitored for signs of anaphylaxis for at least 1 hour following completion of the infusion in an appropriate area with readily available resuscitation equipment and medications (as per protocol section 9.1.2). Patients will be treated for about 6 ½ weeks during this phase (33 daily fractions of radiation therapy and 6 weekly doses of cetuximab).

Cetuximab is to be given every 7 days (+/- 2 days). Cetuximab does not need to be given on Day 1 of each week.

The dose of cetuximab will be rounded off to the nearest 10 mg.

There will be no dose modification of the radiation therapy for toxicity. For dose modifications of cetuximab see section 9.3 below.

9.1.1 RADIATION THERAPY GUIDELINES

Technique:

All radiotherapy techniques are permitted including 3D conformal, IMRT and proton therapy. Lateral fields may be used for diffuse pontine tumors though 3D target definition is recommended.

Dose and volume: All tumors will be treated to 5940 cGy in 33 once daily 180 cGy fractions.

The initial PTV for high-grade gliomas will be determined by adding a 2 cm margin to the area of T1 enhancement (GTV) based on the pre-operative MRI scan. For non-enhancing tumors, the MRI sequence that best defines the extent of disease should be used. A conedown to the post-operative tumor bed, including any residual disease plus a 1cm margin is allowed at 5400 cGy.

The GTV for diffuse pontine tumors will consist of the tumor best demonstrated on MRI. The MRI sequence that best defines the extent of disease should be used. A 1 cm margin is added in all directions to determine the PTV.

Volumes and doses may be modified as necessary to prevent overdosing of critical normal tissues such as spinal cord and optic chiasm, based on institutional practices.

The dose and source will be documented in the Case Report Forms.

Radiation must be performed at a POETIC institution or at a designated academic or professional partner institution, according to standard institutional practice for patients on clinical trials. Radiation may not be performed at a local or private facility that is not a partner for academic purposes.

9.1.2 CETUXIMAB ADMINISTRATION

Strong consideration should be given to antihistamine premedication prior to cetuximab to try to reduce the risk of a hypersensitivity reaction. Diphenhydramine (1 mg/kg IV or orally) is recommended.

Cetuximab will be administered as an intravenous infusion over about 60 minutes +/- 10 minutes, and must be administered at a POETIC institution. The infusion rate should not exceed 10 mg/minute (5 ml/minute). Patients should be carefully monitored for signs of anaphylaxis for at least 1 hour following completion of the infusion in an appropriate area with readily available resuscitation equipment and medications.

9.2 SECOND PHASE: IRINOTECAN & CETUXIMAB

Between 28 and 56 days after completion of radiation therapy (based on the discretion of the investigator and resolution of compromising radiation-induced toxicities) patients will begin irinotecan and cetuximab. To begin this phase of therapy, the ANC must be $\geq 1000/\text{mcl}$, the platelet count $\geq 100,000/\text{mcl}$, and the total bilirubin $\leq 2.0 \text{ mg/dL}$. Patients who cannot begin the second phase of therapy within 56 days will be considered study failures and will be removed from the study and not replaced.

Irinotecan will be administered at a dose of 16 mg/m²/day IV over about 60 minutes ± -10 minutes x 5 consecutive days x 2 weeks every 21 days. Cetuximab will be administered at a dose of 250 mg/m²/dose IV over 60 minutes ± -10 minutes weekly x 3 weeks per cycle (see section 9.12 for administration instructions). The dose of cetuximab will be rounded off to the nearest 10 mg and the dose of irinotecan to the nearest 1 mg. These doses of irinotecan and cetuximab were determined to be safe and tolerable in the POETIC phase I study (CA225085). On days when both irinotecan and cetuximab are administered, the cetuximab will be administered first and the irinotecan infusion will begin about 60 minutes following completion of the cetuximab infusion. Cetuximab is to be given every 7 days (± -2 days). Cetuximab does not need to be given on Day 1 of each week.

Subsequent cycles of irinotecan will begin 21 days following the start of the previous cycle if the ANC is \geq 1000/mcl, the platelet count is \geq 100,000/mcl, and there has been adequate resolution of any other toxicity. If adequate recovery has not taken place by day 21, the start of the cycle will be delayed until sufficient recovery. If the cycle must start more than 28 days following the start of the prior cycle the dose modification section below should be consulted. Patients are intended to receive 10 cycles unless a criterion for removal from study is met (section 13.0). However, for patients whose disease remains stable or better at the completion of 10 cycles,

therapy may be continued at the discretion of the patient and physician until a criterion for removal from the study is met.

The cetuximab must be administered at a POETIC center, but the irinotecan may be administered at another center or via homecare if such a regimen is more convenient for the patient. In such cases, adequate documentation must be sent to the Data and Coordinating Center at MSKCC in a timely fashion and in compliance with all study guidelines and requirements. Local institutions will be responsible for securing all documentation as required on the Case Report Forms regarding irinotecan administration.

9.3 CHEMOTHERAPY/BIOLOGIC DOSE MODIFICATION RULES

9.3.1 CETUXIMAB

Management of Infusion Reactions

Severe infusion reactions require the immediate interruption of cetuximab therapy and permanent discontinuation from further treatment. Appropriate medical therapy including epinephrine, corticosteroids, intravenous antihistamines, bronchodilators, and oxygen should be available for use in the treatment of such reactions. Patients should be carefully observed until the complete resolution of all signs and symptoms.

In previous clinical trials, mild to moderate infusion reactions were managed by slowing the infusion rate of cetuximab and by continued use of antihistamine pre-medications (eg, diphenhydramine) in subsequent doses. If the patient experiences a mild or moderate (Grade 1 or 2) infusion reaction, the infusion rate should be permanently reduced by 50%. For grade 1 or 2 reactions manifesting only as delayed drug fever, see paragraph below. Cetuximab should be immediately and permanently discontinued in patients who experience severe (Grade 3 or 4) infusion reactions.

Treatment of Isolated Drug Fever

[figure not shown]
In the event of isolated drug fever, the investigator must use clinical judgment to determine if the fever is related to the study drug or to an infectious etiology.

If a patient experiences isolated drug fever, for the next dose, pre treat with acetaminophen or non-steroidal anti-inflammatory agent (investigator discretion), repeat antipyretic dose 6 and 12 hours after cetuximab infusion. The infusion rate will remain unchanged for future doses.

If a patient experiences recurrent isolated drug fever following premedication and post-dosing with an appropriate antipyretic, the infusion rate for subsequent dosing should be 50% of previous rate. If fever recurs following infusion rate change, the investigator should assess the patient's level of discomfort with the event and use clinical judgment to determine if the patient should receive further cetuximab.

Management of Pulmonary Toxicity

In the event of acute onset (grade ≥ 2) or worsening pulmonary symptoms which are not thought to be related to underlying cancer, cetuximab therapy should be interrupted and a prompt investigation of these symptoms should occur. Cetuximab retreatment should not occur until

these symptoms have resolved to grade 1. If interstitial lung disease is confirmed, cetuximab should be discontinued and the patient should be treated appropriately.

Management of rash

Grade 3 Acneform Rash/ desquamation	Cetuximab	Outcome	Cetuximab Dose Modification
1st occurrence	Delay infusion 1 to 2 weeks	Improvement	Continue at 250 mg/m ²
		No Improvement	Discontinue cetuximab
2 nd occurrence	Delay infusion 1 to 2 weeks	Improvement	Reduce Dose Level -1
		No Improvement	Discontinue cetuximab
3rd occurrence	Delay infusion 1 to 2 weeks	Improvement	Reduce to Dose Level -2
		No Improvement	Discontinue cetuximab
4th occurrence	Discontinue cetuximab		

Cetuximab Dose Modification Guidelines

Cetuximab Dose Levels

	Weekly Cetuximab dose			
Starting dose	250 mg/m^2			
Dose Level -1	200 mg/m^2			
Dose Level -2	150 mg/m^2			

Cetuximab in Combination with Radiation Therapy

Cetuximab in combination with radiation therapy should be used with caution in patients with a history of coronary artery disease, congestive heart failure, and arrhythmias. Although the etiology of these events is unknown, close monitoring of serum electrolytes, including serum magnesium, potassium, and calcium, during and after cetuximab therapy is recommended.

Management of Hypomagnesemia

Hypomagnesemia has been reported with Cetuximab when administered as a single agent and in combination with multiple different chemotherapeutic regimens. The incidence of hypomagnesemia (both overall and severe [NCI CTC grades 3 & 4]) is increased in patients receiving chemotherapy and Cetuximab as compared with those receiving chemotherapy alone based on controlled clinical trials. Patients receiving Cetuximab therapy should be monitored for hypomagnesemia. Magnesium repletion may be necessary based on clinical judgment.

9.3.2 IRINOTECAN

- GI Toxicity: Grades 3 or 4 despite maximal medical management will mandate a dose reduction by 2 mg/m²/day.
- Hepatic impairment: Irinotecan should not be administered if the total bilirubin is > 2 mg/dL. It may be restarted if the total bilirubin falls to ≤ 2 mg/dL.
- If a cycle cannot start by day 28 due to hematopoietic toxicity (ANC < 1000 and/or platelet count < 100,000), the dose of irinotecan should be reduced by $2 \text{ mg/m}^2/\text{day}$.

9.4 SUPPORTIVE CARE

Clinical judgment may be used to alter the following guidelines without being a protocol violation:

During all phases of therapy

Anti-emetics may be used.

Filgrastim (G-CSF) may be used according to institutional practice and/or ASCO guidelines.

Patients developing dermatologic toxicities while receiving cetuximab should be monitored for the development of inflammatory or infectious sequelae, and appropriate treatment of these symptoms initiated. Dose modifications of any future cetuximab infusions should be instituted in case of severe (grade 3) acneform rash/desquamation (section 9.3.1). Treatment with topical and/or oral antibiotics should be considered; topical corticosteroids are not recommended. If a patient experiences severe acneform rash/ desquamation, cetuximab treatment adjustments should be made according to the table above (section 9.3.1). In patients with mild and moderate skin toxicity, treatment should continue without dose modification.

During the second phase of therapy (while patients are receiving irinotecan)

Anti-convulsants: Enzyme-inducing anti-convulsants (phenytoin, phenobarbital, carbamazepine) should be avoided. Patients who require an anti-convulsant should be treated with a non-enzyme inducing anti-convulsant for a minimum of 4 half-lives of the anti-convulsant agent prior to starting treatment with irinotecan. Documentation of this should be included on the Concomitant Medication form in the Case Report Forms.

Diarrhea: Prophylaxis with an oral cephalosporin (such as cefixime 8 mg/kg/day, maximum 400 mg/day) may be used [J Clin Oncol 2006; 24:563-570]. For early onset diarrhea (during irinotecan infusion or shortly after the infusion), consider atropine (0.01 mg/kg, maximum 0.4 mg) and octreotide. For later onset diarrhea, consider prompt use of loperamide, and consider octreotide if that does not adequately control diarrhea. Suggested loperamide (1 caplet = 2 mg, 1 teaspoon = 5 ml = 1 mg) dosing follows:

- Patients > 43 kg: Take 4 teaspoons or 2 caplets after the 1st loose bowel movement followed by 2 teaspoons or 1 caplet every 2 hours. During the night the patient may take 2 caplets every 4 hours rather than 1 caplet every 2 hours.
- Patients > 30 to 43 kg: Take 2 teaspoons or 1 caplet after the 1st loose bowel movement followed by 1 teaspoon or ½ caplet every 2 hours. During the night the patient may take 1 caplet every 4 hours rather than ½ caplet every 2 hours.
- Patients > 20 to 30 kg: Take 2 teaspoons or 1 caplet after the 1st loose bowel movement followed by 1 teaspoon or ½ caplet every 3 hours. During the night the patient may take 1 caplet every 4 hours rather than ½ caplet every 3 hours.
- Patients > 10 to 20 kg: Take 1 teaspoon after the 1st loose bowel movement followed by 1 teaspoon every 3 hours. During the night the patient may take 1 teaspoon every 4 hours rather than every 3 hours.
- Patients 8 to 10 kg: Take 1 teaspoon after the 1st loose bowel movement followed by ¹/₂ teaspoon every 3 hours. During the night the patient may take ³/₄ teaspoon every 4 hours rather than every 3 hours.

Pneumocystis carinii (PCP) prophylaxis: Patients should receive PCP prophylaxis, according to any standard regimen chosen by the attending pediatric oncologist in agreement with local standard practices, and an individual patient's medication compatibility profile and compliance determination.

10.0 EVALUATION DURING TREATMENT/INTERVENTION

The mandated observations are summarized in Appendix 2.

During the first phase of therapy (Radiation therapy with cetuximab)

Physical exams will be performed and potassium, calcium, and magnesium levels will be obtained once a week, prior to each cetuximab infusion.

CBC and other laboratory work will be obtained as clinically indicated.

[figure not shown]
During the second phase of therapy (irinotecan with cetuximab)

Physical exams will be performed and a CBC, potassium, calcium, magnesium, total bilirubin, AST, and creatinine will be obtained prior to each cycle. Laboratory work during a cycle will be obtained as clinically indicated.

Assessment of tumor status via brain MRI will be performed about 3 weeks after completing RT (pre-cycle 1 chemotherapy), then during every 3^{rd} cycle of irinotecan-cetuximab (during cycles 3, 6, and 9).

Following completion of therapy

For patients who complete protocol therapy and remain on study progression-free, MRI scans of the brain will be performed at about 3, 6, 9, 12, 18, 24, 30, 36, and 42 months post-completion of therapy or until the patient has been removed from the study. Subsequent scans will be performed at the clinician's discretion and are not mandated by this protocol, but are recommended approximately annually.

Mandated evaluations including lab work and MRI scans may be performed at other (non-POETIC) centers if deemed clinically indicated as long as they are submitted to the POETIC investigator in a timely fashion.

10.1 TUMOR TISSUE ANALYSES

Analysis of EGFR and associated molecules HER2 and HER3 expression

[figure not shown]
Although over-expression of EGFR was not shown to be predictive for cetuximab response in previous studies, it cannot be assumed that it will not be predictive in pediatric patients with high-grade glial tumors. We will therefore screen tumor samples for EGFR gene amplification, and EGFR protein over-expression. HER2 and HER3 heterodimerize with EGFR to affect EGFR activity, and HER2 has previously shown some value in predicting cetuximab response. We will therefore study HER2 and HER3 gene amplification and over-expression in tumor specimens. Both procedures will be performed on paraffin sections of tumor (5 micron thickness). To ensure consistency of results between specimens received from different institutions we recommend a standardized fixation procedure, but this is a guideline only and institutional practices may be substituted. Tissue samples will be dissected to a thickness of no greater than 5 mm and fixed in 10% NBF 24-48 hours. Samples will then be transferred to 70% ethanol where they can remain indefinitely with no deterioration of antigen. All subsequent experimentation will be performed at a single institution, the University of Colorado Denver (UCD), to ensure consistency of results.

Gene amplification will be assessed using fluorescence in-situ hybridization (FISH). This procedure requires fifteen paraffin sections per tumor sample. FISH will be performed at the University of Colorado Cancer Center DNA Core facility, managed by [name]. This core facility has relevant experience in that it has performed standardized FDA approved FISH analysis of EGFR, HER2 and HER3 in previous cetuximab lung cancer clinical trials.

Gene over-expression will be assessed using immunohistochemistry (IHC). IHC will be performed by IHCtech (www.ihctech.net), an IHC dedicated facility located on the UCHSC campus that routinely performs standardized staining for EGFR and HER2 in clinical samples.

Analysis of surrogate biomarkers predictive for cetuximab and RT or irinotecan response

To identify surrogate predictors of response to cetuximab and RT or irinotecan, we will perform a global gene analysis of tumor specimens using microarray technology. We will generate gene expression profiles for 50,000 genes for each patient's tumor, and then compare the profiles of those patients who responded to treatment against those who did not respond. This analysis may provide a small number of genes whose expression, or lack thereof, accurately predicts response to therapy. The Pediatric Neuro-oncology Laboratory at UCHSC has performed similar analyses in the identification of prognostic genes for ependymoma recurrence [J Neuro-Oncol 2006; 78:41-46]. Cetuximab-predictive genes identified using gene-expression microarrays would be validated by Western blot analysis and IHC. For microarray and Western blot analyses we would require at least 6 mm3 of tumor tissue, snap frozen in liquid nitrogen at the time of surgery. This would provide a sufficient quantity and quality of RNA and protein to perform the proposed analyses. Fifteen paraffin sections will be required for IHC validation of specific microarray results.

Analysis of MGMT expression

MGMT promoter methylation status has been shown to influence both survival and response to therapy in pediatric glioblastoma multiforme [Pediatr Blood Cancer 2006; 48:403-407]. MGMT methylation status of patients enrolled in this clinical trial will be studied. This procedure requires 1 microgram of DNA, preferably obtained from snap frozen tumor, but also retrievable from paraffin embedded material. In addition, MGMT expression will be measured by IHC.

Data Analysis

Data obtained by FISH, IHC, microarray analysis and MGMT methylation analysis will be analyzed to identify therapeutic response correlates. The biological data can be correlated to response both to the RT-cetuximab and irinotecan-cetuximab as response data to both modalities will be potentially evaluable on this study. These data will help to elucidate the anti-tumor mechanisms of cetuximab in high-grade gliomas of childhood. Correlates of response may also help to select patients with high-grade astrocytomas for treatment with cetuximab in future clinical trials.

The data obtained from these studies directly on high grade gliomas will be correlated with the CSF proteomics data (described below). This will hopefully provide additional insight into the biology of the diffuse pontine gliomas, which is clearly lacking in the literature at this time.

Table of material requirements

Submission of paraffin material is mandatory for high-grade gliomas outside the pons and optional for diffuse pontine gliomas. Submission of the number of paraffin section below is encouraged, but patients will not be excluded from the study if fewer samples or less material are available. Submission of frozen tumor material is strongly encouraged, but not mandatory for study participation.

Analysis	Technique	Tissue requirement per patient
EGFR, HER2, HER3 gene amplification	FISH	12 paraffin sections (5 micron thickness)
EGFR, HER2, HER3 protein overexpression	IHC	
Microarray gene expression analysis and subsequent Western blot analysis	Affymetrix U133+2 microarray analysis and Western blot	6 mm ³ of tumor snap frozen immediately at resection
IHC analysis subsequent to microarray results	IHC	3 paraffin sections (5 micron thickness)
MGMT methylation analysis	Methylation specific PCR	2 mm ³ of tumor snap frozen immediately after resection

Specimen collection

These samples should be forwarded via FedEx, Monday through Thursday to the following address:

Attn: [name] [name]

No weekend deliveries are permitted. Sites should contact [contact] to notify of shipment.

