While cetuximab has been approved for the treatment of metastatic colorectal cancer and head and neck cancer, and has shown promise in treating a number of other solid tumors either as a single agent or in combination with other treatments, EGFR over-expression was found to be non-predictive for cetuximab response [Mol Cancer Ther 2006; 5:104-113]. The over-expression of EGFR has, therefore, not been used as an inclusion criterion in clinical trials of cetuximab. Consequently, there is interest in alternative predictors of response to cetuximab. These molecular predictors could be used to select patients who may have a better response to cetuximab whilst sparing those patients who will not respond to ineffective therapy.

The laboratory investigations described in Section 10.1 will be performed using tumor specimens from patients enrolled in this trial in order to identify predictive markers for response to this regimen. Cetuximab, in combination with RT and/or irinotecan, may prove to be effective in a fraction of the patients treated, and the goal of this objective is to identify a target or targets whose expression pattern predicts treatment response.

3.11 CSF PROTEOMICS (Project leaders: [name], Children's Healthcare of Atlanta, Atlanta, GA & [name], Children's National Medical Center, Washington, DC)

Current diagnostic and therapeutic monitoring of brain tumor patients are significantly hindered due to limited understanding of brain tumor biology and response to therapy. The majority of CNS tumors cannot be identified or followed by expression of serum or CSF markers. However, if available, such markers would be highly desirable and could be used to:

- Detect minimal residual disease
- Predict response to specific targeted therapies
- Distinguish tumor recurrence from post surgical changes or post-radiation changes on neuroimaging
- Augment current histopathologic classification systems
- Improve current clinical and pathological treatment stratification schemata
- Assess efficacy of and tumor response to specific biologic targeted therapies that may not impact tumor size as a primary tumor endpoint (e.g., small molecule inhibitors or anti-angiogenic strategies)

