14.3 SECONDARY BIOLOGICAL AIMS

14.3.1 Progression free and overall survival will be calculated using the methods of Kaplan and Meier, separately for the diffuse pontine and high-grade groups. The response rates will be provided along with their 95% confidence intervals for all patients receiving any study medication or radiation.

14.3.2 It is not known how many patients will agree to participate in the components of the study involving (1) correlation of molecular markers and tumor response to therapy, (2) CSF proteomics, and (3) serum inflammatory cytokine levels. These endpoints are exploratory in nature and any analyses will be purely descriptive. Continuous endpoints will be summarized using medians and ranges, categorical data will be tabulated. Changes in measurements will be given in terms of percent change from baseline and change in absolute value.

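### The 50,000-gene responder comparison has no rule limiting false selections, and its validation step confirms measurement, not prediction in new patients (minor)

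*Combined protocol and SAP*

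**What the plan says.** Section 10.1 states: "We will generate gene expression profiles for 50,000 genes for each patient's tumor". It will then "compare the profiles of those patients who responded to treatment against those who did not respond". The hoped-for result is: "This analysis may provide a small number of genes whose expression, or lack thereof, accurately predicts response to therapy". The follow-up step is: "Cetuximab-predictive genes identified using gene-expression microarrays would be validated by Western blot analysis and IHC".

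The materials table in section 10.1 gives one frozen piece per patient to a single row, "Microarray gene expression analysis and subsequent Western blot analysis". A separate row gives paraffin sections to IHC that follows the array. Paraffin is mandatory for high-grade gliomas outside the pons and optional for pontine tumors. Frozen tissue is encouraged but optional for all.

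Two outcomes are open under Data Analysis in section 10.1: "The biological data can be correlated to response both to the RT-cetuximab and irinotecan-cetuximab". The same paragraph says that correlates may help choose patients for later cetuximab trials. Section 3.10 gives the purpose of the laboratory work: "in order to identify predictive markers for response to this regimen".

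Section 14.3.2 covers this component by name: "These endpoints are exploratory in nature and any analyses will be purely descriptive". It provides medians and ranges, tabulations, and changes from baseline. Neither 10.1 nor 14.3 names a test, threshold, false discovery rate, permutation, cross-validation, hold-out set or independent cohort for the array comparison.

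**The concern.** Reducing 50,000 genes to a small set needs a selection rule, and medians and ranges are not one. Whatever rule is used, the genes at the top of so long a list will look better in the tumors that chose them than they would elsewhere.

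The planned validation does not address this. A second assay on the same tumor can expose a faulty array reading. It cannot expose a chance association: a gene whose expression happens to differ between these few responders and non-responders should differ again on the blot. The step therefore cannot support a statement that a gene predicts response.

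At stake is how secondary objective 2 is read. A reader who sees genes reported as predictive and validated may carry them into patient selection for a later trial on evidence that this design cannot provide.

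**Working it through.** The plan gives no sample size, threshold or error rate for the array comparison, so it has no figure of its own to reproduce.

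**Inputs from the documents.**
- Genes: 50,000 (10.1).
- High-grade astrocytoma cohort: 26 patients (14.1.2). This caps that cohort's tumors, and optional frozen tissue can only lower the number.
- Pontine tumors: usually not biopsied (3.11), so they add few specimens.
- Number taking part in the biology component: stated to be unknown (14.3.2).

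**Assumed.** The number of tumors with array data, *n*, and of responders among them, *k*. A range is shown because the documents give neither.

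**Perfect separation by one unrelated gene.** If expression is unrelated to response and there are no ties, every placement of the *k* responders among the *n* ranks is equally likely. Two placements separate the groups completely, one in each direction. The probability is 2/C(*n*,*k*), and the expected count is 50,000 × 2/C(*n*,*k*). This expectation does not need the genes to be independent.

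| Responders of tumors | C(*n*,*k*) | Expected unrelated genes separating perfectly |
|---|---|---|
| 4 of 16 | 1,820 | 54.9 |
| 5 of 20 | 15,504 | 6.4 |
| 5 of 26 | 65,780 | 1.5 |
| 8 of 20 | 125,970 | 0.8 |
| 8 of 26 | 1,562,275 | 0.06 |
| 13 of 26 | 10,400,600 | 0.01 |

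**A less extreme standard.** From the exact Mann-Whitney null distribution, in either direction, the expected number of unrelated genes with AUC of at least 0.90 is about 271 (5 of 20), 172 (5 of 26), 30 (8 of 26) and 9 (13 of 26).

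**Several genes combined.** 50,000 independent, normally distributed, unrelated genes were simulated, with ten runs per setting. The ten with the largest t-statistics formed a nearest-centroid rule. Scored on the same tumors, balanced accuracy was 99.7% to 100% in all six settings (3 of 12, 4 of 15, 5 of 20, and 5, 9 and 13 of 26). On new tumors it was about 50%, which is chance.

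**Two outcomes.** If the search is run for both treatment phases, the expected counts of the two searches add.

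**Why the test must be named in any fix.** With a rank test at 5 of 20, the smallest two-sided p-value is 2/15,504 = 0.000129. Benjamini-Hochberg at 10% selects *m* genes only if the *m*-th smallest p-value is at most 0.10 × *m*/50,000. Setting 0.10 × *m*/50,000 ≥ 0.000129 gives *m* ≥ 64.5. About 65 genes would have to separate perfectly before any was selected, so a rank test is too coarse at this size.

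**The case against.** The strongest reply is that the plan already limits its claims. Secondary objective 2 speaks of exploring potential associations, section 4.0 lists the component as optional and exploratory, and 14.3.2 makes the analysis descriptive. No p-value is planned, so a count of genes passing 0.05 would describe a test that the plan never specifies. The text is hedged, and no go/no-go or stopping rule uses the gene list. This stands, and it is why the point is minor. It does not supply a selection rule, and it does not fit the wording in 10.1 about accurate prediction and validation.

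Second, validation may simply mean assay confirmation; 10.1 itself speaks once of IHC validation of array results. That is a fair reading, but the sentence quoted above applies the word to genes already labelled predictive.

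Third, a reader might infer that all validation is done on exactly the tumors that chose the genes. The documents support this for the Western blot only. Because paraffin is mandatory and frozen tissue optional in high-grade astrocytoma, IHC could include patients without array data. The documents do not say whether it would, and they plan no separate test of prediction in such patients.

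Fourth, every tumor and responder count is assumed, and at 8 or more responders of 26 a perfect single-gene separator by chance is unlikely. This also stands.

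**Conclusion.** The concern holds as a minor point. As written, 10.1 and 14.3.2 contain nothing that limits false selections from 50,000 genes, and the stated validation confirms measurement without testing prediction in new patients.

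The size depends on unstated numbers. Chance alone would be expected to supply between about 55 perfect separators (4 of 16) and 0.06 or fewer (8 or 13 of 26). AUCs of 0.90 or more arise by chance in every setting for which they were calculated, about 30 genes at 8 of 26 and 9 at 13 of 26. The ten-gene simulation assumes independent normal genes; the expected counts do not.

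A reader might go further and infer that noise is bound to yield perfectly predictive genes, that any resulting list could not be told from chance, or that the protocol commits future trials to it. The documents do not support this. Perfect separation is unlikely in part of the plausible range, a strong true signal could stand out, and the text says only that correlates may help with later selection. The primary endpoint, its decision rules and the toxicity rule are unaffected.

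**What to change.** 1. In 14.3.2, state that the array comparison is hypothesis-generating. Rank genes by a moderated t-test, separately for each response outcome used, and report Benjamini-Hochberg false discovery rates. Analyze any biopsied pontine tumors separately or as a stratum.
2. Report prediction accuracy, if at all, only from cross-validation in which gene selection is repeated inside every fold.
3. In 10.1, replace the wording on accurate prediction and the label Cetuximab-predictive with candidate. Describe Western blot and IHC as confirmation of measurement, and state that prediction needs an independent cohort.

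The cost is SAP and protocol wording plus analysis code, with no new samples, visits or patients. The downside is that the reported list may well be empty.
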